### **End of Study**

The end of the treatment period is defined as the date when the last patient, last visit (LPLV) at 96 weeks occurs (*or at Week 100 in the substudy*).

### **Length of Study**

The total length of the *study* is expected to be approximately 4 years from the first patient enrolled to LPLV.

The end of study is defined as the LPLV of the safety follow-up.

### **Investigational Medicinal Products**

#### **Test Product (Investigational Drug)**

Dose 1 of ocrelizumab will be administered as two 300-mg IV infusions (600 mg total) separated by 14 days (i.e., Days 1 and 15). Subsequent doses will be administered as one 600-mg IV infusion every 24 weeks, for a maximum of 4 doses.

#### **Non-Investigational Medicinal Products**

Premedicate with 100-mg methylprednisolone (or equivalent) completed approximately 30 minutes prior to each ocrelizumab infusion and with an antihistaminic drug (e.g., diphenhydramine) approximately 30 – 60 minutes before each infusion of ocrelizumab to reduce the frequency and severity of infusion-related reactions (IRRs).

The addition of an antipyretic (e.g., acetaminophen/paracetamol) may also be considered to further reduce the frequency and severity of IRRs.

### **Statistical Methods**

#### **Primary Efficacy Outcome Measures**

The primary efficacy assessment will be the proportion of patients who are free of any protocol-defined events during a 96-week period. The definition of a protocol-defined event is the occurrence of at least one of the following while on treatment with ocrelizumab:

- A protocol-defined relapse
- A T1 Gd-enhanced lesion on brain MRI
- A new and/or enlarging T2 lesion on brain MRI
- Confirmed disability progression (24 weeks)

### **Determination of Sample Size**

Assuming a) the expected proportion of patients who will be event free during 96 weeks is 45%; b) the type one error rate is 5% and the half-width of 95% confidence interval (CI) for the proportion is 4%; c) the probability that half-width of 95% CI is at most 4% is 80%, then the required sample size will be n=600.

### **Interim Analyses**

It is estimated that two to three interim analyses will be performed during the course of the study, according to patient enrollment and availability of data of interest. Interim analyses may be used for internal decision making, hypothesis generation, abstraction/publication for major MS conferences, or other purposes, as applicable. Details on the timing and scope of interim analyses will be described in the Statistical Analysis Plan

## Appendix 2

### Schedule of Assessments

| Visit Number                                      | Screening       | Treatment Period |                  |                    |                    |                    |                    | End of Treatment/
Early Withdrawal Visit b | Unscheduled Visit
(due to relapse) c | Safety Follow-up Visit d |
|---|-----------------|------------------|------------------|--------------------|--------------------|--------------------|--------------------|--|--|-------------------------------------|
|   | 1               | 2                | 3                | 4                  | 5                  | 6                  | 7                  |  |  |                                     |
| Week  | -4 a | -                | 2                | 24                 | 48                 | 72                 | 96                 |  |  |                                     |
| Study Day (window in days)                        | -28             | 1
Baseline    | 15
( $\pm$ 2) | 169
( $\pm$ 14) | 337
( $\pm$ 14) | 505
( $\pm$ 14) | 673
( $\pm$ 14) |  |  |                                     |
| Informed consent e                     | x               |                  |                  |                    |                    |                    |                    |  |  |                                     |
| Medical history and demographic data f | x               |                  |                  |                    |                    |                    |                    |  |  |                                     |
| Review inclusion and exclusion criteria           | x               | x                |                  |                    |                    |                    |                    |  |  |                                     |
| Physical examination g                 | x               | x                | x                | x                  | x                  | x                  | x                  | x  | x  |                                     |
| Height  | x               |                  |                  |                    |                    |                    |                    |  |  |                                     |
| Weight  | x               |                  |                  |                    |                    |                    |                    |  |  |                                     |
| Vital signs h                          | x               | x                | x                | x                  | x                  | x                  | x                  | x  |  |                                     |
| Laboratory Assessments i               |                 |                  |                  |                    |                    |                    |                    |  |  |                                     |
| Hematology, chemistry, urinalysis j    | x               | x k   |                  | x                  | x                  | x                  | x                  |  |  |                                     |
| Pregnancy test l                       | x               | x                | x                | x                  | x                  | x                  | x                  |  | x  |                                     |
| Hepatitis screening m                  | x               |                  |                  |                    |                    |                    |                    |  |  |                                     |
| Hepatitis B virus DNA test m           | x               |                  |                  | x                  | x                  | x                  | x                  |  |  |                                     |
| Immunoglobulin levels n                | x               |                  |                  | x                  | x                  | x                  | x                  |  |  | x                                   |
| Lymphocyte subtypes o                  | x               |                  |                  | x                  | x                  | x                  | x                  |  |  | x                                   |

Ocrelizumab—Genentech, Inc.

36/Statistical Analysis Plan MN30035

| Visit Number                                      | Screening       | Treatment Period |             |               |               |               |                | End of Treatment/
Early Withdrawal Visit b | Unscheduled Visit
(due to relapse) c | Safety Follow-up Visit d |
|---|-----------------|------------------|-------------|---------------|---------------|---------------|----------------|--|--|-------------------------------------|
|   |                 | 1                | 2           | 3             | 4             | 5             | 6              |  |  |                                     |
| Week  | -4 a | -                | 2           | 24            | 48            | 72            | 96             |  |  |                                     |
| Study Day (window in days)                        | -28             | 1
Baseline    | 15
(± 2) | 169
(± 14) | 337
(± 14) | 505
(± 14) | 673
(± 14)  |  |  |                                     |
| EDSS score  | x               | x k   |             | x             | x             | x             | x              | x  |  |                                     |
| Neurological examination p             | x               | x                | x           | x             | x             | x             | x              | x  | x  | x                                   |
| Patient-Reported Outcome Assessments q |                 | x                |             | x             | x             | x             | x              |  |  |                                     |
| Brain MRI r                            |                 | x s   |             | x             | x             |               | x b |  |  |                                     |
| Recording of potential relapses                   |                 | x                | x           | x             | x             | x             | x              | x  | x  | x                                   |
| Adverse event assessment t             |                 | x                | x           | x             | x             | x             | x              | x  | x  | x                                   |
| Concomitant treatment review                      |                 | x                | x           | x             | x             | x             | x              | x  | x  | x u                      |
| Methylprednisolone premedication v     |                 | x                | x           | x             | x             | x             |                |  |  |                                     |
| Ocrelizumab administration w           |                 | x                | x           | x             | x             | x             | x              |  |  |                                     |

β-hCG = beta human chorionic gonadotropin; eCRF = electronic Case Report Form; EDSS = Expanded Disability Status Scale; HBcAb = hepatitis B core antibody; HBsAg = hepatitis B surface antigen; HBV = hepatitis B virus; HepCAb = hepatitis C antibody; IRR = infusion-related reaction; IV = intravenous; MRI = magnetic resonance imaging; MS = multiple sclerosis; PCR = polymerase chain reaction; PML = progressive multifocal leukoencephalopathy; PRO = patient-reported outcome; QC = quality control.

a The screening period will last up to 4 weeks, but it may be prolonged for up to 8 weeks for relevant clinical, administrative, or operational reasons.

b When a patient discontinues treatment, all assessments must be completed/obtained, except for MRI if done within the past 8 weeks unless clinically indicated.

c Additional assessments may be conducted, as determined by the investigator, in order to investigate adverse events.

- d The Safety Follow-up Period will begin when the patient completes the study and does not continue with commercially available ocrelizumab, or discontinues from treatment early. Patients will be assessed in Safety Follow-up every 24 weeks for 48 weeks counting from the date of the last infusion of ocrelizumab. After 48 weeks, if the peripheral blood B-cell count remains depleted, monitoring of the patient should continue at 24-week intervals until the B-cell count has returned to the baseline value or to the lower limit of the normal range, whichever is lower. During the Safety Follow-up Period, patients who receive other B-cell targeted therapies will only be followed for an additional period of approximately 48 weeks from the start of the alternative MS treatment; they will not be entered into the prolonged B-cell monitoring period thereafter.*
- e Written informed consent will be obtained from all patients during screening in order to be eligible for the study.*
- f Medical history includes clinically significant diseases, surgeries, reproductive status, smoking history, and all medications (e.g., prescription drugs, over-the-counter drugs, herbal or homeopathic remedies, and nutritional supplements) used by the patient within 4 weeks prior to the screening visit. Demographic data will include age, sex, and self-reported race/ethnicity.*
- g A full physical examination will be conducted at the screening and early termination visits. At all other visits, a limited physical examination will be conducted. Any abnormality identified at baseline should be recorded on the eCRF. Changes from baseline abnormalities should be recorded at each subsequent physical examination. New or worsened clinically significant abnormalities should be recorded as adverse events, if appropriate.*
- h Vital signs will include the measurements of heart rate, systolic and diastolic blood pressures, and temperature. Vital signs should be taken within 45 minutes prior to the premedication methylprednisolone infusion. In addition, vital signs should be obtained prior to the ocrelizumab infusion then every 15 minutes for the first hour, followed by every 30 minutes until 1 hour after the end of the infusion.*
- i Needs to be available prior to dosing (to be taken up to 14 days prior to dosing). In rare cases in which the result is not assessable (e.g., indeterminate) or is abnormal, the tests need to be repeated. Any abnormal screening laboratory value that is clinically relevant should be retested in order to rule out any progressive or uncontrolled underlying condition.*
- j Hematology will include hemoglobin, hematocrit, RBCs, WBC absolute and differential, ANC, and quantitative platelet count. Chemistry will include AST, ALT, GGT, total bilirubin, urea, uric acid, creatinine, potassium, sodium, calcium, and phosphorus. Urinalysis or urine dipstick will be used to assess kidney function.*
- k If the screening assessments have been conducted/obtained within 14 days prior to dosing, respective baseline assessments do not need to be repeated prior to dosing.*
- l Serum  $\beta$ -hCG must be performed at screening in women of childbearing potential. Subsequently, urine  $\beta$ -hCG (sensitivity  $>25$  mIU/mL) must be collected. On infusion visits, the urine pregnancy test should be performed prior to methylprednisolone infusion in all women of childbearing potential. If positive, ocrelizumab should be withheld and pregnancy status confirmed.*
- m All patients must have negative HBsAg result and negative HepCAb screening tests prior to enrollment in the study. If the total HBcAb is positive at screening, HBV DNA measured by PCR must be negative in order for a patient to be eligible for the study. For enrolled patients with negative HBsAg and positive total HBcAb, HBV DNA (by PCR) must be repeated every 24 weeks.*
- n Immunoglobulin levels collected only and stored for further analysis upon request.*

- o Whole-blood samples will be collected to determine the duration of B-cell depletion and recovery (CD19+) and T-cell counts (CD4+, CD8+).
- p Neurological examinations will be used to distinguish relapse in MS from another neurological (non-MS) disorder. Potential relapses should be recorded throughout the treatment period. Investigators will also screen patients for signs and symptoms of *worsening neurological function* localized to the cerebral cortex, such as cortical symptoms/signs, behavioral and neuropsychological alteration, retrochiasmal visual defects, hemiparesis, cerebellar symptoms/sings (e.g., gait abnormalities, limb incoordination). Patients with suspected PML should be withheld from ocrelizumab treatment until PML is ruled out by complete clinical evaluation and appropriate diagnostic testing (see Appendix 6). A patient with confirmed PML should be withdrawn from the study.
- q PRO assessments will consist of the following: Multiple Sclerosis Impact Scale 29 (MSIS-29), the Treatment Satisfaction Questionnaire for Medication (TSQM II), and the Treatment Satisfaction with Medicines Questionnaire (SATMED-Q). *Please note that all PROs are required to be administered prior to administration of study drug and prior to any other study assessment(s) to ensure the validity of the instruments is not compromised.*
- r Should only be done at scheduled visits unless PML is suspected.
- s *MRI has to be conducted before the baseline visit, and results must be available prior to treatment. Prior to initiation of treatment on Day 1/Baseline, a QC report for the baseline MRI scan must have been received from the centralized reading center confirming scan passed QC.*
- t After informed consent has been obtained but prior to initiation of study drug, only serious adverse events caused by a protocol-mandated intervention (e.g., invasive procedures such as biopsies, discontinuation of medications) should be reported. After initiation of study drug, *related serious adverse events must be collected and reported regardless of the time elapsed from the last study drug administration, even if the study has been closed. Unrelated serious adverse events must be collected and reported during the study through the end of the Safety Follow-up period, which is at least 48 weeks after the last infusion but may be extended in patients whose B cells take longer to replete. Non-serious adverse events have to be reported until the end of the Safety Follow-up Period.*
- u *Medications used after treatment discontinuation should be recorded during the Safety Follow-up Period.*
- v All patients must receive prophylactic treatment with 100 mg methylprednisolone (or equivalent), administered by slow IV infusion, to be completed approximately 30 minutes before the start of each ocrelizumab infusion. Prophylactic treatment with an analgesic/antipyretic (e.g., 1 g acetaminophen) and/or an IV or oral antihistamine (e.g., IV diphenhydramine 50 mg or equivalent dose of alternative) is strongly recommended 30–60 minutes prior to the start of ocrelizumab infusion to reduce the risk of IRRs.
- w Dose 1 of ocrelizumab will be administered as two 300-mg IV infusions (600 mg total) separated by 14 days (i.e., Days 1 and 15). Subsequent doses will be administered as one 600-mg IV infusion every 24 weeks for a maximum of 4 doses.

## Appendix 3

### Data Handling Rules

#### **Assessment of clinical relapse:**

1. Check whether the following eCRF question is answered 'yes': "Did suspected MS relapse symptoms persist for > 24 hours and were not being attributable to confounding clinical factors? (e.g. fever, infection, injury, adverse reactions to concomitant medication"
2. Check whether the first EDSS assessment at a visit (unscheduled or scheduled) on or after the onset date of the relapse is increased by  $\geq 0.5$  steps from the previous EDSS; OR SELECTED FSS domains relevant to the relapse event (pyramidal, ambulation, cerebellar, brainstem, sensory, or converted visual) are increased by  $\geq 2$  points on one domain or  $\geq 1$  point on two or more domains. When deriving this step do the following:
  - Select the last EDSS/FSS score before each clinical relapse onset date
  - Select the first EDSS/FSS score on or after each clinical relapse onset date
  - Calculate the difference between the two scores above
3. Select clinical relapses where there is an increase of  $\geq 0.5$  in EDSS OR  $\geq 2$  on one appropriate FSS domain OR  $\geq 1$  on two or more appropriate FSS domains

For each relapse that satisfies the 3 criteria above, check if the following relapses are within 30 days (i.e., the onset dates are  $\leq 30$  days apart). If they are within 30 days, then the later relapses are not protocol-defined relapses

Additional data handling rules are specified throughout the document and in DAP Module 2.

## **Appendix 4** **Programming Codes for Statistical Analyses**

Kaplan-Meier method

```
proc lifetest data=dataset method=km conftype=loglog outsurv=surv  
plots=none notable STDERR;  
    time aval*eventyn(1);  
run;
```

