### **Time-to-event endpoints**

The Kaplan–Meier method (i.e., the product limit estimator) will be used to estimate the time to onset of the 5 parameters listed below. Kaplan-Meier plots will be produced. The event-free probability at Week 96 will be calculated based on Kaplan-Meier method as sensitivity analyses of the primary endpoint, proportion of patients without a protocol-defined event.

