#### Time to protocol-defined event

For patient with an event, it will be defined as the earliest onset time of the following: a protocol-defined relapse, T1 Gd-enhanced lesion, new and/or enlarging T2 lesion, or confirmed disability progression (see below for the determination of the time to onset of confirmed disability progression)

Patients without an event (either during the complete 96-week study period, or before early withdrawal from treatment) will be censored at the last evaluation of a protocol defined event, i.e. the maximum time of last MRI or EDSS evaluation

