#### Time to onset of first relapse

For patients with an event, it will be determined as the first relapse time reported by the patient.

Patients without any relapse will be censored at the last study visit.

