#### Time to onset of first T1 Gd-enhanced lesion

For patient with event, it will be defined as the first time a T1 Gd-enhanced lesion was detected post baseline.

Patients without an event will be censored at the last performed MRI evaluation.

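### The SAP's Kaplan-Meier code makes EVENTYN=1 the censored value but never defines EVENTYN; if 1 means event, it contradicts the SAP's censoring rules and inverts the time-to-event results

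*SAP*

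**What the plan says.** SAP Section 4.4.2 (Time-to-event endpoints) says that the Kaplan-Meier method "will be used to estimate the time to onset of the 5 parameters listed below". It gives the method a second use: "The event-free probability at Week 96 will be calculated based on Kaplan-Meier method as sensitivity analyses of the primary endpoint".

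The censoring rules in the same section all point one way:

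- **Time to protocol-defined event:** patients without an event "will be censored at the last evaluation of a protocol defined event, i.e. the maximum time of last MRI or EDSS evaluation".
- **First relapse:** "Patients without any relapse will be censored at the last study visit".
- **First T1 Gd-enhanced lesion:** "Patients without an event will be censored at the last performed MRI evaluation". The rule for new or enlarging T2 lesions is the same.
- **Confirmed disability progression:** patients without an event are censored at their last available EDSS.

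SAP Appendix 4 supplies the only Kaplan-Meier code. It opens with "proc lifetest data=dataset method=km conftype=loglog outsurv=surv", and its TIME statement begins "time aval*eventyn(1", followed by the closing bracket. EVENTYN appears nowhere else in either document. The end of SAP Appendix 3, just before this code, says: "Additional data handling rules are specified throughout the document and in DAP Module 2". DAP Module 2 is not among the documents.

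**The concern.** In PROC LIFETEST the values in brackets after the status variable are the censoring values, so the printed line tells SAS that EVENTYN=1 is a censored observation. A variable with that name would ordinarily be 1 for a patient who had the event. A programmer who codes it by its name and copies the line would censor each patient with an event at the event time, and would count each event-free patient as failing at the last assessment.

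The curves and medians would then describe time to an event-free last assessment, not time to disease activity. SAS would give no error message. At stake are the five secondary time-to-event endpoints and the Week 96 sensitivity estimate of the primary endpoint. Time to treatment discontinuation (SAP Sections 4.2 and 4.7.1) would be affected too if the same code is reused for it.

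**Working it through.** The documents state no Kaplan-Meier result, so there is no figure to reproduce. The check sets code against text, then sizes the consequence on illustrative data.

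**Step 1: code against text.**

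| Coding of EVENTYN | Censored by the printed line | Censored by SAP 4.4.2 | Agreement |
|---|---|---|---|
| 1 = event | patients with an event | patients without an event | contradiction |
| 1 = censored | patients without an event | patients without an event | consistent |

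**Step 2: inputs.** From SAP Section 2.3: N = 600 and 45% event free at Week 96. Assumed, because the documents do not give them: first events at Weeks 24/48/72/96 in the ratio 50/20/10/20, nominal visit times and, initially, no dropout.

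This gives 330 events (165, 66, 33 and 66) and 270 event-free patients followed to Week 96.

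**Step 3: events counted as events.**

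- S(48) = (600 − 165 − 66)/600 = 0.615
- S(96) = 270/600 = 0.450

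**Step 4: the printed line with 1 = event.** All 330 events become censored, and nobody fails before Week 96, so S(48) = S(72) = 1.000. At Week 96 the risk set is 66 + 270 = 336, of whom 270 count as failures:

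- S(96) = 1 − 270/336 = 66/336 = 0.196

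In general, without dropout, if p is the event-free share and q is the share of patients whose first event is at Week 96, the inverted estimate is q/(p + q). Here that is 0.11/(0.45 + 0.11) = 0.196.

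**Step 5: sensitivity.** With p = 0.45 the correct value is always 0.45, but the inverted one moves with event timing:

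- q = 0.07: 0.07/0.52 = 0.135
- q = 0.17: 0.17/0.62 = 0.274

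With the 50/20/10/20 pattern and other event-free shares, where the dropout columns censor 60 event-free patients early (20 each at Weeks 24, 48 and 72) and hold the number of events fixed:

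| Event-free share | Correct S(96), no dropout | Inverted S(96), no dropout | Correct S(96), 60 dropouts | Inverted S(96), 60 dropouts |
|---|---|---|---|---|
| 30% | 0.300 | 84/264 = 0.318 | 0.249 | 0.348 |
| 45% | 0.450 | 66/336 = 0.196 | 0.417 | 0.207 |
| 55% | 0.550 | 54/384 = 0.141 | 0.526 | 0.146 |

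The error has no fixed direction: at 30% event free the inverted figure is slightly too high, and at 45% and 55% it is far too low. With 1 = censored, the printed line returns the correct columns.

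**The case against.** A reader might infer that the SAP's Kaplan-Meier results are bound to be inverted. The documents do not support that. Neither document says what EVENTYN=1 means, and the coding may be given in DAP Module 2. The code is a generic template with a placeholder dataset name, while the written censoring rules are explicit and correct. This stands, and it is why the point is conditional.

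A reader might also infer that an inversion would pass unnoticed. That goes too far. Protocol Section 6.5.4 requires the proportions with an event and censored to be reported, and a reversal would swap them. The SAP also reports event-free proportions at Weeks 24 and 48, against which a curve at or near 1.000 would look wrong. These outputs would probably expose the error. The Week 96 figure alone might not: 0.318 against 0.300 would not look odd.

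Thirdly, editing the line to `eventyn(0)` straight away could do harm. If the dataset uses 1 = censored, that edit would create the very error it is meant to remove. This also stands and sets the order of the fix.

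The objections do not remove the defect. On one coding the line is wrong. On the other, the SAP prints code with an undefined indicator whose name suggests the opposite of its meaning, and a second programmer working independently from the SAP could make the same mistake.

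**Conclusion.** The point holds conditionally. If EVENTYN=1 means event, the only Kaplan-Meier code in the SAP contradicts Section 4.4.2 and inverts the five secondary time-to-event analyses and the Week 96 sensitivity estimate. The illustrative size is about 0.20 instead of 0.45, assuming 45% event free, no dropout and 11% of patients with a first event at Week 96. Only the 45% comes from the documents, and the size and direction change with event timing. If 1 means censored, no result changes and the defect is one of naming and documentation.

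A reader might take this as a threat to the primary result, but it is not. The primary analysis is a proportion with a Clopper-Pearson interval (SAP Section 4.4.1) and does not use this code. The negative binomial models for relapses and lesion counts and the MMRM analyses do not use it either.

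**What to change.** 1. Establish how EVENTYN is coded in the analysis dataset before editing anything.
2. State that coding in SAP Appendix 4.
3. Align the line with the censoring rules in Section 4.4.2. If 1 = event, use `time aval*eventyn(0);`. If 1 = censored, rename the variable as a censoring flag, for example `time aval*cnsr(1);`.
4. Check the production program before the final analysis, including time to treatment discontinuation if it uses the same code.

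The cost is one line of code, one sentence of definition and a program check. No data collection or endpoint definition changes.
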